1.0 Objectives

The primary objective is to assess the activity of the combination of the Bruton's tyrosine kinase (Btk) inhibitor PCI-32765 and rituximab in patients with high-risk Chronic Lymphocytic Leukemia (CLL) and Small Lymphocytic Lymphoma (SLL). For this study, we define high-risk CLL as any CLL patient who has a 17p deletion or an 11q deletion or a TP53 mutation. We define high-risk SLL as any SLL patient who has a 17p deletion or an 11q deletion or a TP53 mutation. Alternatively, any patient with a diagnosis of CLL or SLL who had a short remission duration of less than 3 years after prior first-line chemo-immunotherapy would be considered a high-risk CLL or SLL patient, regardless of the presence or absence of any chromosomal marker. The secondary objective is to assess the tolerability of the combination of PCI-32765 and rituximab in CLL/SLL patients.

2.0 Background

2.1 Chronic Lymphocytic Leukemia (CLL)

CLL is the most common form of adult leukemia in the United States. It has been estimated that there are approximately 150,000 individuals living with CLL in the United States. The use of combination of chemo-immunotherapy as initial therapy is associated with high response rates. Unfortunately, once disease relapse has been observed, second line treatment is less effective and response durations are shorter. An alternative to repeating chemo-immunotherapy is to use the monoclonal antibody alemtuzumab. Alemtuzumab is able to induce a response in up to 30% of the patients, but is associated with significant immunosuppression and infections. Also, it lacks activity in patients that have developed bulky lymphadenopathy (larger than 5 centimeters)¹. Combination of purine-analogue based regimens have limited activity: the combination of fludarabine, cyclophosphamide, rituximab, alemtuzumab (CFAR) is associated with an overall response rate of 65% in patients that have received prior therapy and once patients are fludarabine refractory their median survival is less than twelve months based on our published experience ².

2.2 High-risk genetic abnormalities (17p deletion, 11q deletion, TP53 mutation). Standard treatment approaches such as chemo-immunotherapy (e.g., fludarabine/cyclophosphamide/rituximab or FCR) are highly effective in frontline treatment of the majority of CLL patients. However, there is a small, challenging

subgroup of patients whose leukemia is characterized by presence of 17p deletion or *TP53* mutation who respond poorly to chemo-immunotherapy^{3, 4} or other treatment modalities for CLL. Related to the poor treatment outcome in this high-risk subgroup, patients with 17p deletion or *TP53* mutation have a short median life expectancy of less than 2 to 3 years⁵. Accordingly, there is an urgent need for alternative therapeutic strategies acting independently of p53 for patients with a 17p deletion or *TP53* mutation, both in the frontline and salvage setting. Because of the poor outcome and responses to standard therapy, patients with 17p deletion or *TP53* mutation will not be required to have received prior therapy to enroll.

CLL patients with del(11q22–11q23) represent another challenging clinical subset. This genomic aberration occurs in approximately 20% of patients with advanced CLL. These patients are usually younger than the typical CLL patient (median age: 59 years), and often have extensive lymphadenopathy at the time of diagnosis. The clinical course of patients with the 11q deletion is usually characterized by rapid disease progression with shorter treatment-free survival; a shorter overall survival has been reported in patients younger than 55 years. Although patients with 11q deletion have an improved progression-free survival (PFS) with chemo-immunotherapy, remission duration and overall survival of patients in this subgroup indicate that patients with 11q deletion have an inferior outcome compared with patients with favorable genomic abnormalities⁶.

Patients with short remission duration after frontline chemo-immunotherapy, for example with the FCR regimen, constitute another high-risk group of CLL patients⁶, and oftentimes such patients also display high-risk cytogenetic abnormalities (del17p, del11q). Such patients typically have low response rates and remission durations when re-treated with chemo-immunotherapy⁶.

The preliminary experience with PCI-32765 in relapsed CLL patients with 17p deletion, 11q deletion, or *TP53* mutation indicates that PCI-32765 displays high clinical activity in this risk group. An analysis presented at the 2010 annual meeting of the American Society of Hematology (ASH) showed that single agent treatment with PCI-32765 induces 30% partial remissions (PR, n=3), 30% partial remissions with lymphocytosis (PR with lymphocytosis, n=3), and stable disease in 30% (SD, n=3) of CLL patients with 17p deletion, which is similar to the response rates for CLL patients without 17p deletion. Treatment was discontinuation in only one out of 10 patients with 17p deletion⁷. These data are

based on a relatively short median follow-up time (2 to 8 months), but nonetheless are highly promising and therefore should be verified in a larger cohort of CLL patients. Therefore, to address this unmet medical need and to generate more robust experience with PCI-32765 in high-risk CLL patients, we propose to examine the activity of PCI-32765 and rituximab in 40 CLL patients with high-risk disease features which have relapsed disease.

2.2 PCI-32765

Antigenic stimulation through the B cell antigen receptor (BCR) promotes the expansion of chronic lymphocytic leukemia (CLL) and other malignant B cells ^{8,9}. Bruton's tyrosine kinase (Btk), a key component of BCR signaling, can be blocked by PCI-32765, a small-molecule Btk inhibitor, that displayed activity in patients with CLL and other B cell malignancies in the first clinical trial ⁷. PCI-32765 is a potent (IC₅₀, 0.5 nM) and selective Inhibitor of Btk that binds covalently to a cysteine residue (Cys-481) in the active site of Btk, leading to irreversible inhibition of the enzymatic activity of Btk ¹⁰. Once daily oral dosing results in 24-hour sustained target occupancy. In vitro studies demonstrated that inhibition of Btk in CLL cells results in the blockade of BCR related survival signals, thereby causing apoptosis ¹¹. Additionally, [name] laboratory has demonstrated that inhibition of Btk with PCI-32765 markedly decreases CLL cell responses to chemotactic factors elaborated by stromal cells, such as CXCL12 and CXCL13, resulting in diminished CLL cell migration and homing capabilities ¹¹.

A recent analysis of 38 CLL patients from an ongoing Phase Ib/II trial of single-agent PCI-32765 in CLL or SLL included patients with relapsed or refractory disease following at least 2 treatment regimens, and a cohort of patients over 65 years old with treatment naïve disease ⁷. When measured clinically and by CT scan every 2 months, patients treated with PCI-32765 typically had an immediate and marked nodal response; 87% of patients with evaluable nodal disease achieved a nodal response. There have been no cases of primary lymph node progression. For the Phase Ia trial with a median follow-up of 8 months, there were 13 evaluable patients with 1 CR (8%), 8 PRs (62%) and 2 patients with a nodal response with lymphocytosis (15%). Two additional patients had stable disease. There have been only 3 patients with disease progression, and an additional 3 patients discontinued treatment for reasons other than progressive disease. Of 32 evaluable patients in the Phase Ib study

(with less than 2 months median follow-up) there were 8 PRs (25%) and an additional 17 patients with a nodal response with lymphocytosis. An additional two patients have stable disease. As such, the overall response rate (ORR) from the Phase Ib/II trial experience at this point is 38% (1 CR, 16 PRs in 45 patients).

94% patients experienced an adverse event (AE), 38% patients experienced an adverse event grade 3 or greater in severity (nausea, vomiting, fatigue, diarrhea, headache, rash). The incidence of \geq grade 3 adverse events believed to be related to PCI-32765 was 17%. 14 patients experienced a serious adverse event (SAE), with “serious” defined as requirement for hospitalization. 6 SAE were considered related to study drug by the investigator. These were one case of viral lymphadenitis, one case of a subdural hematoma, one case of viral infection (follow-up reported as unrelated), one case of decreased appetite, dehydration, and asthenia, one case of sepsis, and one case of headache and dizziness (follow-up reported as unrelated viral vestibular neuritis)⁷. Two patients in this pooled analysis have died due to progressive disease.

Diarrhea, nausea, and fatigue have been the most commonly reported adverse events, with most of the reported events occurring early in treatment (cycles 1 or 2). Significant myelosuppression has been infrequent; with grade 3 or greater thrombocytopenia or neutropenia reported in less than 5% of patients. Significant hepatic or renal toxicity has been absent. In addition, with longer-term follow-up, there has been no evidence of cumulative toxicity, either overall, or related to specific events. Because of a) one event of spontaneous subdural hematoma in a patient who took ibuprofen and PCI-32765 at the time of detection of the subdural hematoma, and b) the controversial role of Btk in platelet function and aggregation, we initiated clinical and laboratory assessment of platelet function of patients treated with PCI-32765 on the ongoing Phase I/II trial. There have been no subsequent bleeding events; some patients, however, displayed petechiae or bruises. Therefore, we will implement regular clinical and laboratory assessment and exclude patients with a history of bleeding diathesis or coagulopathy, recent surgical procedure, stroke, or hemorrhage, and patients receiving Coumadin.

2.2 Rituximab

Rituximab is a monoclonal antibody that binds to the human CD20 antigen. Rituximab has been extensively used for the treatment of chronic lymphoproliferative disorders. As a single agent, it is able to induce a response in

up to 30% of the patients with relapsed CLL and is synergistic with chemotherapy agents and other monoclonal antibodies when used in combination¹². The rationale for combining PCI-32765 with rituximab is to potentiate the clinical efficacy of these agents without increasing their toxicity. This is based on the different mechanisms of action and the non-overlapping toxicity profile. When used as single agent, PCI-32765 typically induces a “compartment shift” of CLL cells from the tissues into the peripheral blood⁷. Clinically, this is associated with a transient surge in lymphocyte counts and lymph node shrinkage during the first weeks of treatment. Because of this lymphocytosis, the patients treated with single agent PCI-32765 often times do not achieve remissions, even though they are asymptomatic and display partial or complete responses at other disease sites. To improve the efficacy of PCI-32765, rituximab is an ideal combination partner, because this antibody is very effective in clearing the blood stream of CLL cells, but less effective at eradicating disease in lymphatic tissues and bone marrow. As such, this protocol combines two agents with complementary single agent activity in different disease sites: PCI-32765 has remarkable activity in the lymphatic tissues, and rituximab is highly effective in clearing the blood stream of CLL cells.

The side effect profile of these two agents also appears to be entirely different and non-overlapping; the toxicity of rituximab consists mainly of infusion reactions, nausea and late transient myelosuppression. PCI-32765 has a very benign side effect profile with low-grade gastrointestinal side effects, no signs of any cumulative toxicity, and no immunosuppression or myelosuppression.

3.0 Study Design

This is a single center open label phase II study to evaluate the efficacy and safety of the combination of PCI-32765 and rituximab in patients with high-risk CLL and SLL who have received prior treatment. Pharmacyclics will supply PCI-32765, commercial supply of rituximab will be used for this study. PCI-32765 will be supplied as capsules containing 140 mg of PCI-32765.

4.0 Treatment Plan

Rituximab (375 mg/m²) will be given intravenously on Day 1, Day 8 (+/- 3 days), Day 15 (+/- 3 days), and Day 22 (+/- 3 days), and then continued once every 4 weeks only on Days 1 (+/- 7 days) during cycles 2 - 6 (+/- 7 days), see Study Calendar, unless patients experience toxicities that warrant early discontinuation

of the rituximab (as determined by the treating physician). There will be no dose modifications of rituximab. PCI-32765 will be started on Day 2 of cycle 1 at a dose of 420 mg (3 x 140-mg capsules) orally once daily with 8 ounces (approximately 240 mL) of water (avoid GRAPEFRUIT JUICE due to CYP450 3A4 inhibition) and will be continued daily. There will be no dose modifications of PCI-32765. The doses and schedule of PCI-32765 is based on prior studies with this drug in patients with CLL and other B cell malignancies. At this dose, the target enzyme, Btk, is fully inhibited. The rituximab doses and schedule are considered standard for treatment of CLL patients. A subject diary will be used to aid with PCI-32765 administration compliance. Treatment duration will be 12 cycles, and it will be possible to continue beyond 12 cycles if there is a significant benefit such as an ongoing PR or CR. Response will be evaluated after three, six and twelve cycles. (Each cycle consists of 28 days, see Study Calendar).

Rituximab should be held for any Grade 4 toxicity or for any rituximab-related, clinically significant, unmanageable Grade 3 adverse events. Rituximab should be held until the adverse event returns to baseline or resolves complete. PCI 32765 should be held for any Grade 3 toxicity. PCI-32765 should be held until the adverse event returns to baseline or resolves complete. After Cycle 1, if PCI-32765 is held for > 28 days, the subject should be discontinued from the study.

Special Handling Instructions

Allopurinol at the dose of 300mg daily will be given during the first one to two weeks of treatment as standard tumor lysis prophylaxis. Unused or expired PCI-32765 will be disposed per institutional policy.

Concomitant Medication: Patients receiving Coumadin are ineligible to participate in this study. Patients who recently received Coumadin must be off this medication for at least 7 days prior to start of the study.

PCI-32765 is metabolized by CYP3A4/5 and CYP2D6. Therefore strong inhibitors of CYP3A4/5 and CYP2D6 are prohibited. Once patients are on study they may acquire an illness that requires concomitant therapy with a drug that inhibits these CYPs. In such cases, alternatives to strong CYP3A4/5 inhibitors (such as clarithromycin, ketoconazole, itraconazole, nefazodone, and ritonavir) and strong CYP2D6 inhibitors (such as bupropion, fluoxetine, paroxetine, and quinidine) should be sought if possible, for example milder CYP inhibitors.

A comprehensive list of cytochrome P450 isoenzymes and CYP3A4/5 and CYP2D6 inhibitors, inducers, and substrates can be found at <http://medicine.iupui.edu/flockhart>. This website is continually revised and should be checked frequently for updates.

Concomitant Use of QT Prolonging Agents

During the course of study drug treatment medications known to cause Torsades des Pointes should be avoided. Medications known to cause QT prolongation may be used with caution.

Concomitant Use of Antiplatelet Agents and Anticoagulants

- Laboratory studies have shown that, in vitro, PCI-32765 can prevent platelets from aggregating normally; the clinical significance of this finding is unknown at this time. While serious bleeding has been uncommon in patients treated to date, it is possible that treatment with the study drug could increase the risk of bruising or bleeding, particularly in subjects receiving other antiplatelet agents or anticoagulants.
- Subjects receiving antiplatelet agents in conjunction with PCI-32765 should be observed closely for any signs of bleeding or bruising, and PCI-32765 should be withheld in the event of any bleeding events.
- Subjects requiring the initiation of anticoagulation with warfarin or related agents during the course of the study should have treatment with PCI-32765 held, and PCI-32765 should not be restarted until subjects are stably anticoagulated. During the co-administration of PCI-32765 and anticoagulant therapy, the INR should be monitored carefully and subjects should be observed closely for signs and symptoms of bleeding.

For the following hematologic toxicities:

- Grade 4 ANC (< 500/ μ L) for > 7 days
- Grade 3 or 4 Platelets (< 50,000/ μ L) in presence of significant bleeding
- Grade 4 Platelets (< 25,000/ μ L)

Gastrointestinal toxicities:

- Grade 3 or 4 nausea, vomiting or diarrhea if persistent despite optimal antiemetic and/or anti-diarrheal therapy)

or any other grade 4 or unmanageable grade 3 toxicities:

Occurrence	Action
1 st	Hold PCI-32765 until recovery to Grade ≤ 1 or baseline; may restart at original dose level
2 nd	Hold PCI-32765 until recovery to Grade ≤ 1 or baseline; restart at one dose level lower (280 mg daily)
3 rd	Hold PCI-32765 until recovery to Grade ≤ 1 or baseline; restart at one dose level lower (140 mg daily)
4 th	Discontinue PCI-32765

Antiemetics are permitted if clinically indicated. Standard supportive care medications are permitted.

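### Section 4.0 bars any change to the PCI-32765 dose, yet its toxicity table orders 280 mg after the 2nd and 140 mg after the 3rd qualifying event, and nothing says which rule governs

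*Combined protocol and SAP*

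**What the plan says.** All of the relevant text is in section 4.0 (Treatment Plan).

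The opening paragraphs set the starting dose at 420 mg once daily, taken as three 140 mg capsules, and state: "There will be no dose modifications of PCI-32765". They then give a hold rule, "PCI 32765 should be held for any Grade 3 toxicity", and a recovery rule, "PCI-32765 should be held until the adverse event returns to baseline or resolves complete". Once Cycle 1 is over, a hold of more than 28 days takes the patient off study.

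Later in the section, after the advice on antiplatelet agents and anticoagulants, come a list of hematologic and gastrointestinal toxicities, the catch-all "or any other grade 4 or unmanageable grade 3 toxicities", and a table of actions by occurrence:

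- 1st: hold until Grade ≤ 1 or baseline, then "may restart at original dose level".
- 2nd: "Hold PCI-32765 until recovery to Grade ≤ 1 or baseline; restart at one dose level lower (280 mg daily".
- 3rd: the same hold, then "restart at one dose level lower (140 mg daily".
- 4th: "Discontinue PCI-32765".

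The opening paragraphs do not refer to the table, and the table does not refer back to them.

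**The concern.** A required cut to 280 mg or 140 mg is a dose modification on any ordinary reading, and the opening paragraphs rule out dose modifications. For a patient whose 2nd or 3rd qualifying event has fully resolved, staff cannot comply with both texts.

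The patients concerned have had repeated serious or unmanageable toxicity, so the question is whether they are re-exposed at full dose or at a reduced one. Whichever dose is given departs from one of the two texts, so protocol deviations cannot be classified consistently.

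**Working it through.** The plan gives no figure to reproduce here. The check sets the two texts side by side.

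**Inputs, all from sections 3.0 and 4.0:** starting dose 420 mg daily; capsule strength 140 mg; table doses 280 mg and 140 mg; hold limit 28 days after Cycle 1.

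**Step 1: the dose implied by the opening paragraphs.** They name no restart dose. With a 420 mg starting dose and no modification allowed, 420 mg is the only dose left for a patient who restarts. This is an inference, but a direct one.

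**Step 2: comparison by occurrence, event fully resolved.**

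| Occurrence | Opening paragraphs | Table | Gap | Table dose / 420 | Dose conflict? |
|---|---|---|---|---|---|
| 1st | 420 mg (3 capsules) | 420 mg permitted (3 capsules) | 0 | 1 | No |
| 2nd | 420 mg (3 capsules) | 280 mg (2 capsules) | 420 − 280 = 140 mg | 280/420 = 0.667 | Yes |
| 3rd | 420 mg (3 capsules) | 140 mg (1 capsule) | 420 − 140 = 280 mg | 140/420 = 0.333 | Yes |
| 4th | silent on a 4th event | stop | not a dose comparison | – | No |

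**Step 3: the table's scope.** Its position after the anticoagulant advice might suggest that it applies only to patients on those drugs. Its list does not fit that reading: it covers prolonged neutropenia, nausea, vomiting and diarrhea, and the catch-all takes in all other Grade 4 and unmanageable Grade 3 events. It is a general toxicity table.

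**Step 4: recovery thresholds.** The opening paragraphs require a return to baseline or complete resolution. The table accepts Grade ≤ 1 or baseline. The two differ for a patient whose baseline was Grade 0 and whose event has improved to Grade 1 but no further. Under the table the hold can end; under the opening paragraphs it continues. After Cycle 1, if the residual persists beyond 28 days, that patient is on treatment under one text and off study under the other. This can happen at the 1st, 2nd or 3rd occurrence. At the 1st the table only permits a restart, so holding longer breaks neither text, but the consequence for the 28-day count is the same.

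**Step 5: hold triggers.** The opening paragraphs hold for any Grade 3 event; the table's list is narrower. A broad hold rule can sit over a narrower list that governs counting and dose, so this difference is not a contradiction.

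**The case against.** The strongest reply is that the specific governs the general. The table is graded by occurrence and names exact doses. The opening sentence belongs to the description of planned dosing and mirrors the one for rituximab. Most clinicians would probably follow the table. That is a reasonable guess, but the protocol does not say it. The opening paragraphs can also be read as a complete scheme: they give their own hold, recovery and discontinuation rules, and add that Btk is fully inhibited at this dose, which can be taken as a reason for keeping it fixed. What stands of the reply is that the table is the likelier intention, which supports the direction of the fix.

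A reader might infer more than the documents support:

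- *That the 4th occurrence is the largest conflict, 420 mg against none.* Stopping a drug is not a dose modification, and the opening paragraphs themselves provide for discontinuation. The table adds a rule that is compatible with them.
- *That many patients will be affected.* Section 2.2 reports that 38% of earlier single-agent patients had an event of Grade 3 or higher. That is not a rate of qualifying events, still less of repeat ones. The documents give no such rate.
- *That the operating characteristics are undermined.* Tables 1 and 2 and the toxicity stopping rule in section 10.0 do not depend on which restart dose is used.

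**Conclusion.** The PCI-32765 dosing rule is wrong as written for the 2nd and 3rd qualifying occurrences. The two texts differ by 140 mg and 280 mg a day, so the table gives two-thirds and one-third of the dose that the opening paragraphs leave available. The conclusion rests on reading a required reduction as a dose modification, and on the absence of any precedence statement in the supplied text.

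The differing recovery thresholds are a subsidiary inconsistency. They matter for patients with a persistent Grade 1 residual, through the 28-day limit. How many patients either point would reach cannot be estimated. This is a matter of patient safety and conduct, not of the statistical design.

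**What to change.** 1. Extend the opening sentence "There will be no dose modifications of PCI-32765" with the words *except as given in the toxicity table*. This resolves the conflict in favor of the reduced doses, the safer choice after repeated toxicity.
2. Use one recovery threshold in both places, for example the table's Grade ≤ 1 or baseline, with the sponsor confirming the choice. This allows a restart with residual Grade 1 toxicity. The stricter threshold would instead carry more patients past the 28-day limit.
3. Keep the hold for any Grade 3 toxicity and the 28-day limit.

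Two alternatives should be avoided. Giving the table's events the looser threshold and all other Grade 3 events the stricter one would make milder events harder to restart from than Grade 4 ones. It would also leave Grade 4 neutropenia of 7 days or less without a clear restart rule. Narrowing the hold to the table's list would lose protection, because that list includes Grade 3 platelets only when there is significant bleeding.

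The cost is a wording amendment, which under section 11.0 needs review by the drug supplier and IRB approval before use. The reduced doses are two and one of the 140 mg capsules already supplied, so no new strength, procedure or patient is needed.

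### Section 4.0 contradicts itself on whether PCI-32765 may be reduced and on when a held dose may restart

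*Combined protocol and SAP*

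**What the plan says.** Both sets of instructions are in Section 4.0 of the combined protocol and SAP.

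The narrative starts PCI-32765 at 420 mg once daily and says "There will be no dose modifications of PCI-32765". On toxicity it says "PCI 32765 should be held for any Grade 3 toxicity" and then "PCI-32765 should be held until the adverse event returns to baseline or resolves complete". It adds a limit: "After Cycle 1, if PCI-32765 is held for > 28 days, the subject should be discontinued from the study".

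Later in the section, a list of events leads into a table of actions by occurrence. The list contains:

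- Grade 4 neutropenia lasting more than 7 days
- Grade 3 or 4 platelets "in presence of significant bleeding"
- Grade 4 platelets
- Grade 3 or 4 nausea, vomiting or diarrhea "if persistent despite optimal antiemetic and/or anti-diarrheal therapy"
- any other Grade 4, or unmanageable Grade 3, toxicity

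For these, the drug is held until Grade 1 or lower, or baseline. It may restart at full dose after the first occurrence, restarts at 280 mg after the second and at 140 mg after the third, and is stopped at the fourth.

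Nothing in the section gives either set precedence.

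**The concern.** A treating physician cannot follow both sets. After a second listed event, one patient could restart at 420 mg and another at 280 mg, each in line with a written instruction. A patient whose event has settled at Grade 1 from a Grade 0 baseline could restart under one sentence and stay on hold under another. After Cycle 1, the second patient would be discontinued once the hold passed 28 days.

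This bears on dose received, on safety and on who remains in the study. Tolerability is the secondary objective in Section 1.0, so dose changes and discontinuations should come from one rule.

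**Working it through.** The protocol gives no figure to reproduce here. The check sets the two instructions side by side.

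**1. Restart dose.** Inputs: 420 mg and no dose modification (Section 4.0, narrative); 280 mg, 140 mg and stop (Section 4.0, table).

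| Listed occurrence | Narrative | Table | Table dose as share of 420 mg |
|---|---|---|---|
| 1st | 420 mg | 420 mg | 100% |
| 2nd | 420 mg | 280 mg | 280/420 = 66.7% |
| 3rd | 420 mg | 140 mg | 140/420 = 33.3% |
| 4th | silent | stop | not applicable |

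The second and third rows contradict. The fourth does not: the narrative sets no occurrence limit, so the table adds a rule there. The narrative says of 420 mg that "At this dose, the target enzyme, Btk, is fully inhibited". The documents give no inhibition figure for 280 or 140 mg, so a pharmacological consequence of the difference cannot be stated.

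**2. Release from hold.** Inputs: baseline or complete resolution (narrative); Grade 1 or lower, or baseline (table).

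| Baseline grade | Current grade | Narrative | Table |
|---|---|---|---|
| 0 | 0 | restart | restart |
| 0 | 1 | hold | restart |
| 0 | 2 or more | hold | hold |
| 1 | 1 | restart | restart |
| 2 | 2 | restart | restart |

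Only the second row conflicts. It arises for Grade 3 events that fall under both instructions, such as diarrhea persisting despite optimal therapy, which is both a Grade 3 toxicity and a listed event. If Grade 1 persists after Cycle 1, the narrative's hold exceeds the limit on day 29 and the patient is discontinued. Under the table, the patient could already have restarted.

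**3. Trigger.** The narrative holds for every Grade 3 toxicity. The list attaches conditions to Grade 3 events but never says that the drug is held only for those. The list can be read as a counted subset inside a general hold. The conditions make that reading uncertain, because they do no work for holding if every Grade 3 event is held anyway. This is an ambiguity.

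**4. Size.** Section 2.2 (PCI-32765) reports single-agent experience: Grade 3 or higher events in 38% of patients, drug-related ones in 17%, and Grade 3 or higher thrombocytopenia or neutropenia in less than 5%. If those rates carried over to 40 patients, the counts would be 0.38 × 40 = 15.2, 0.17 × 40 = 6.8 and fewer than 0.05 × 40 = 2. These are patients with at least one event. The conflicts need a repeat listed event, or an event that settles at Grade 1 from a Grade 0 baseline, and the documents give no rate for either.

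**The case against.** The strongest defense is that a specific table overrides general text. That is a reasonable convention, but the protocol does not state it and its dose sentence has no exception. Nor is that sentence easily read as meaning only no planned changes: the narrative uses the same sentence for rituximab, which has hold rules and no reduction steps anywhere.

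A second defense is that the instructions form two tiers. This reconciles the triggers but not the doses. For release it gives an odd order: a controlled Grade 3 event would have to resolve fully, while an unmanageable Grade 3 or a Grade 4 event could restart at Grade 1.

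A third is that the reach is narrow. This largely stands. Doses agree at the first occurrence, release differs in one configuration, and the discontinuation consequence needs a long hold after Cycle 1. A single center also limits divergence between teams, although Section 7.0 allows some first-month visits at local offices. Even a uniform unwritten convention would breach one written instruction.

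A reader might infer that the list tells physicians to dose through controlled Grade 3 events. It does not say so. Low platelets are a poor example in any case: Section 5.0 excludes only counts below 30,000, so 30,000 to 49,999 can be a patient's baseline, and both rules release at baseline.

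**Conclusion.** The point holds on two matters: whether PCI-32765 may be reduced, and the grade at which a held dose may restart. Per patient, the gap is 420 mg against 280 mg after the second listed event, 420 mg against 140 mg after the third, and hold against restart at Grade 1 from a Grade 0 baseline. The trigger needs clarifying but is not contradictory, and the fourth-occurrence stop is an addition, not a conflict.

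A reader might go further and infer that the PFS or toxicity stopping rules in Section 10.0 are compromised. The documents do not support that: they give no outcome or toxicity data by dose and no rate of repeat events. The conclusion rests on the current text alone and assumes that no precedence rule exists outside it. It justifies a wording correction that the sponsor should make.

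**What to change.** Amend Section 4.0 as follows:

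- Qualify the sentence "There will be no dose modifications of PCI-32765" so that it excepts the changes given in the section's toxicity table.
- Use one release criterion for all toxicity holds: Grade 1 or lower, or baseline, as in the table.
- Keep the narrative's hold as the general rule, reworded to any toxicity of Grade 3 or higher, since it now names only Grade 3.
- State that only the listed events count toward the table's reductions and fourth-occurrence stop. Events held only under the general rule restart at the same dose.
- Keep the 28-day limit, and the separate holds for bleeding on antiplatelet agents and for starting warfarin.

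Two simpler repairs have costs. Dropping the general Grade 3 hold would leave a manageable Grade 3 hemorrhage with platelets of 50,000 or more, in a patient not on antiplatelet agents, without an explicit hold. Section 9.0 classes that event as major hemorrhage, and Section 4.0 notes that in vitro "PCI-32765 can prevent platelets from aggregating normally". Making every Grade 3 or higher event a table trigger would let four brief, controlled events end treatment.

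The clinical cost of the recommended wording is that controlled Grade 3 events may restart at Grade 1 instead of after full resolution. The administrative cost is one amendment, with the company review and IRB approval that Section 11.0 requires. No new data or visits are needed.
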